#### 2. Primary Sponsor: same as above

#### INTRODUCTION AND PURPOSE

The overarching purpose of this study is to further our understanding of the individual and interactive effects of the hormone estrogen and the neurotransmitter serotonin on certain aspects of cognition and brain activation in menopausal women ages 48 to 60 years. Women will undergo cognitive testing and fMRI sessions both before and after 6 weeks of either estrogen or placebo administration. We will recruit women who are across the first 10 years and 11 months since their last menstrual period so that we can gather information regarding the potential impact of time since menopause on our outcomes of interest. We anticipate that findings from this study will help scientist and clinicians to refine their use of estrogen therapy in menopausal women. In addition, should the role of serotonin be of utmost importance for maintenance of healthy cognition, these data aid future drug development to preserve health cognition and/or to treat dementias in which serotonin is an important factor. This proposal is both novel and timely as results from this study are likely to provide information critical to the on-going discussion regarding the risks and benefits of ET use in menopausal women.

The aim of this study is to examine the interactive effects of estrogen and serotonin (5HT) on cognition, emotional processing, and brain activation. We will study the effects of acute tryptophan (TRP) depletion on cognition and mood in healthy menopausal women before and after estrogen replacement treatment (ERT). Using functional magnetic resonance imaging (fMRI), we will identify differences in brain activation during cognitive tasks with and without TRP depletion and before and after ERT in order to determine which brain regions and cognitive functions are affected by each manipulation.

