The results of the proposed study are expected to provide insights regarding the clinical use of estrogen in healthy menopausal women. By examining the effects of estrogen treatment in women within 10 years of their last menstrual period, we aim to evaluate whether estrogen administration can improve certain aspects of cognition in women along the peri- and early menopause stages of life. *While the study proposed in this present application will not provide definitive information regarding 'when' and 'how long' women should use ET for cognitive benefits, it will provide data to guide future investigations. In addition, our findings are expected to further our understanding of the individual and interactive effects of estrogen and serotonin on specific aspects of cognition and brain regions thought to underlie those processes.*  Previous studies have found interactions between treatment with estrogen and with selective serotonin reuptake inhibitors (SSRIs). For example, administration of fluoxetine was found to suppress circulating estradiol levels and estradiol treatment-related enhancement of spatial memory in ovariectomized rats (Taylor et al., 2004). Whether the cognitive changes associated with this drug-hormone interaction were due to changes in estradiol level and/or secondary to primary neuronal effects could not be determined. As these rodents were acutely hypogonadal, it is not known whether the same interaction between SSRI and estrogen would occur with the gradual decline in estrogen characterized by a natural menopause. In the human laboratory, women with hot flashes and depressive symptoms demonstrated a better symptom reduction with low-dose conjugated equine estrogen (CEE) treatment plus fluvoxamine than with CEE treatment alone (Nagata et al., 2005). Whether fluvoxamine alone compared to CEE alone was more effective in the treatment of hot flashes and depressive symptoms was not addressed by the investigators. However, these findings suggest that for women experiencing vasomotor and mood symptoms in the menopause, a regimen that combines estrogen with a SSRI may be preferable.

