## CHARACTERISTICS OF THE STUDY POPULATION

#### 1. Target Population and Accrual

Women from the greater Philadelphia and surrounding areas who are ages 48 – 60 and determined to be peri- or post-menopausal per the following guidelines will be considered for enrollment into this study:

Women will be included in the study if they have a FSH  $\geq$  30 IU/ml and either report that their LMP was at least 12 months prior to presentation (postmenopausal women) OR if they report menstrual cycle irregularity with menstrual cycle length of <24 or > 36 days duration (perimenopausal women). Length of menopause will be used as a continuous variable of number of months since LMP when analyzing performance on cognitive tasks and activation within regions of interest. For women who have previously used HT, months since LMP will be determined as the total length of time since their last menstrual period during which they have not used HT.

We anticipate the composition of the proposed study population to reflect the greater Philadelphia referral base. The projected composition from Philadelphia is African American 42.58%, Hispanic 8.5%, Asian 4.42%, Other 2.04% and White, not of Hispanic Origin, 42.46%. The size of our expected samples will limit our ability to detect effects due to ethnicity or minority status, but we may have sufficient data to begin to examine the impact of ethnicity on estrogen's and serotonin's effects on brain activation. We will make attempts to enhance recruitment of minorities by making sure that fliers and brochures are available at a variety of locations throughout the Philadelphia area as well as promoting a marketing campaign that includes direct home mailings throughout the greater Philadelphia metropolitan area.

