#### 2. Key Inclusion Criteria:

Women ages 48 to 60 (at the time of enrollment) will be eligible for this study if they:

- Have no history of major depressive disorder, generalized anxiety disorder, and or panic disorder within the last three years according to the Structured Clinical Interview for DSM-IV Axis I Disorders (SCID-NP) (First et al., 1995), or a history of major depressive disorder, generalized anxiety disorder, and or panic disorder greater than 3 years ago, but now resolved according to the Structured Clinical Interview for DSM-IV Axis I Disorders (SCID-NP) (First et al., 1995);
- Have no substance abuse disorders (this includes alcohol, prescription, and illicit substances) within the last three years according to the Structured Clinical Interview for DSM-IV Axis I Disorders (SCID-NP) (First et al., 1995);
- Subject has history of substance abuse disorders (this includes alcohol, prescription, and illicit substances) ≥3 years ago but the period of abuse did not last more than 5 years according to the Structured Clinical Interview for DSM-IV Axis I Disorders (SCID-NP) (First et al., 1995);
- 4. No first-degree relative (excluding children) with a known psychotic disorder or bi-polar disorder per patient report. Psychotic disorders include schizophrenia, schizoaffective disorder, psychotic disorder;
- 5. Have not taken hormonal contraceptives, ET or HT for at least 3 months as per self-report;
- 6. Are within 10 years and 11 months of LMP as per self-report;
- Have a follicular stimulating hormone level (FSH) of >30 IU/ml as per hormone testing results; women with an FSH below 30 will have the option to undergo an additional blood draw between 3-9 months following the initial blood draw (see note 2 below);

- 8. Are able to give written informed consent;
- Provide written documentation of having had a normal mammogram and a PAP within the recommended timeframe as defined by the American College of Obstetricians and Gynecologists (ACOG) – please visit their website for current recommendations;
- 10. Must have clear urine toxicology screen upon recruitment;
- 11. Are fluent in written and spoken English;
- 12. Are right-handed.

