# 3. Method for Assigning Subjects to Groups

After completing the first two TRP depletion test sequences, participants will be randomized to receive either treatment with 17β-estradiol (Vivelle Dot® 0.10 - 0.15 mg/day) or a look-alike placebo patch for a total of 8 weeks. The research pharmacist who is responsible for dispensing the estrogen or placebo patches will also be responsible for the randomization of all subjects together with the statistician on the study. Randomization will be blocked and stratified. We will use a block size of 3 to be able to maintain a 2:1 ratio of estrogen to placebo within each stratum. To stratify randomization based upon time since last menstrual period by tertiles (1st=0-40 mos; 2nd=40-80 mos; 3rd=80-120 mos), we will prepare separate randomization tables for each stratum. The research pharmacist, PI, and research project manager will know to which group the subject has been randomized. The research pharmacist, PI or research project manager can be reached at any time should it become necessary to unblind a study participant immediately. The subject and all other study-related personnel (clinicians, raters, fMRI technicians, etc.) will be blind to subject assignment.

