# STUDY PROCEDURES

# 1. Detailed Description

This study involves TRP depletion, evaluation of cognition, and the use of fMRI during cognitive and affective task performance both before and after estrogen or placebo treatment (PT). There will be four successful\* TRP depletion test sequences: two test sequences one week apart prior to ET or PT, and two sequences one week apart following approximately 6-weeks of double-blind ET or PT. Each TRP depletion test day will involve ingestion of 70 capsules. During one of each pair of tests, the 70 capsules will contain 31.5 g of lactose (sham depletion; for participants who are not lactose intolerant) or 31.5 g of microcellulose (sham depletion; for participants who have mild to moderate lactose intolerance), while during the other test they will contain a total of 31.5 g of amino acids, but no tryptophan (see below; Neumeister et al., 2004; Neumeister et al., 2005). The order of the tests (sham vs. active depletion) will be randomly assigned in double blind fashion by the research pharmacist. Imaging procedures will take place on each of the test days. Subjects will be required to remain at the Center for Human Phenomic Science (CHPS) for the entire Test Day except during the fMRI scan.\*\*

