# Randomization to Estrogen Treatment (ET) or Placebo Treatment (PT)

After completing the first two TRP depletion test sequences, participants will be randomized to receive either treatment with 17β-estradiol (Vivelle Dot® 0.10 mg/day) or a look-alike placebo patch for a total of 8 weeks. The research pharmacist who is responsible for dispensing the estrogen or placebo patches will also be responsible for the randomization of all subjects together with the statistician on the study. Randomization will be blocked and stratified. We will use a block size of 3 to be able to maintain a 2:1 ratio of estrogen to placebo within each stratum. To stratify randomization based upon time since last menstrual period by tertiles (1st=0-40 mos; 2nd=40-80 mos; 3rd=80-120 mos), we will prepare separate randomization tables for each stratum. The research pharmacist, PI, and research project manager will know to which group the subject has been randomized. The research pharmacist, PI or research project manager can be reached at any time should it become necessary to unblind a study participant immediately. The subject and all other study-related personnel (clinicians, raters, fMRI technicians, etc.) will be blind to subject assignment.

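### Do randomisation strata that end at 120 months since LMP leave women eligible up to 131 months without an allocation table?

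*Combined protocol and SAP*

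**What the plan says.** Two sections give the same allocation rule, Methods 3 (Method for Assigning Subjects to Groups) and Randomization to Estrogen Treatment (ET) or Placebo Treatment (PT). The plan is to "stratify randomization based upon time since last menstrual period by tertiles", with bands of 0-40, 40-80 and 80-120 months. The last of these reads "80-120 mos), we will prepare separate randomization tables for each stratum". Blocks have size 3 to hold a 2:1 ratio in each stratum. The research pharmacist carries out the randomisation together with the statistician.

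The eligibility limit is longer. Key Inclusion Criteria item 6 reads "Are within 10 years and 11 months of LMP as per self-report", and Introduction and Purpose agrees: "We will recruit women who are across the first 10 years and 11 months since their last menstrual period". The Background describes women "within 10 years of their last menstrual period".

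For previous users of hormone therapy (HT), Target Population and Accrual says that "months since LMP will be determined as the total length of time since their last menstrual period during which they have not used HT". The same section makes length of menopause a continuous variable in the analyses. No section gives a rule for values above 120 months.

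**The concern.** Stratified blocked randomisation needs a rule that places every eligible woman in one table before her allocation is drawn. As printed, the rule does not place a woman at 121 to 131 months, and a woman at exactly 40 or 80 months fits two bands. If table choice is left to discretion, two things could be at stake.

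- **Balance.** Women handled outside the tables would not be blocked, so the arms could differ more in time since LMP. The study regards that variable as important, since H1.2 predicts more benefit from ET in recently menopausal women.
- **Concealment.** The pharmacist, the principal investigator and the project manager know the assignments, and the block size is fixed at 3. Someone who knows the earlier entries in a block can sometimes deduce the next one, so a free choice of table could in principle become a choice of arm.

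**Working it through.** **Inputs.**
- Eligibility limit: 10 years 11 months (Key Inclusion Criteria item 6; Introduction and Purpose).
- Strata: 0-40, 40-80, 80-120 months; blocks of 3 at 2:1 (both randomisation sections).
- Sample: 28 ET + 14 placebo = 42 (Specific Aim 2).
- The documents give no distribution of months since LMP, so two shapes are assumed below.

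**Step 1: size of the gap.** 10 x 12 + 11 = 131 months, and 131 - 120 = 11 months. Whole months 121 to 131 fall in no printed band; 40 and 80 fall in two. HT time is subtracted, so a woman at the limit returns to 120 only with at least 11 months of past HT (131 - 11 = 120). With 10 months of past use she still counts as 121. Some brief HT users are therefore in the gap as well as never-users.

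**Step 2: how many women.**
- Even spread over 0-131: 11/131 = 0.084; 0.084 x 42 = 3.5 women; chance of at least one = 1 - (1 - 0.084)^42 = 0.97.
- Recruitment falling linearly to zero at 131: the tail area is (11/131)^2 = 0.00705; 0.00705 x 42 = 0.30 women; chance of at least one = 1 - (1 - 0.00705)^42 = 0.26.

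The even spread is nearer an upper figure. Entry is limited to "Women ages 48 to 60 (at the time of enrollment", so the oldest eligible woman (60 years 11 months) at 121 months (10 years 1 month) had her LMP at 50 years 10 months. Perimenopausal women near 0 months are also enrolled.

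**Step 3: effect on balance.** Trials of 42 women were simulated with 2:1 blocks of 3 in each table, 20,000 per scheme and spread. The measure is the SD of the ET minus placebo difference in mean months since LMP. The between-woman SD is 131/sqrt(12) = 37.8 months (even) and 131/sqrt(18) = 30.9 months (falling).

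| Women at 121-131 months go into | Even: months (SD units) | Falling: months (SD units) |
|---|---|---|
| third table | 4.95 (0.131) | 4.51 (0.146) |
| separate fourth table | 5.03 (0.133) | 4.84 (0.157) |
| no table, unblocked 2:1 | 7.05 (0.186) | 4.94 (0.160) |

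For scale, a 28:14 split with no stratification gives sqrt(1/28 + 1/14) = 0.327 SD units, which is 37.8 x 0.327 = 12.4 months (even) or 30.9 x 0.327 = 10.1 months (falling). Every scheme in the table is well below that. A fourth table instead of the third costs 0.133 - 0.131 = 0.002 (even) or 0.157 - 0.146 = 0.011 (falling) SD units. Only unblocked allocation under the even spread raises the figure noticeably, and nothing in the protocol suggests that scheme.

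**Step 4: does any analysis use the bands?** Statistical Analysis does not mention them. Months since LMP enters as a continuous variable. The section on randomisation to ET or PT adds control for age and plasma estradiol when effects of time since LMP are examined. H1.2 is posed within the ET group, so it does not depend on balance between arms. Each woman is her own baseline: the Detailed Description has "two test sequences one week apart prior to ET or PT" and two more after about six weeks of treatment. A chance imbalance would matter only if months since LMP alters the ET-versus-placebo change.

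**The case for a change.** The strongest case for a change is that the mismatch is real and repeated. The 120-month bound appears in two sections and the 131-month limit in two others, all of it current text. A complete rule would cost one sentence, and it would remove discretion in a trial where several people know the assignments and the blocks are short.

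The inconsistency stands. The discretion argument is weaker. Tertiles divide the whole range into three, so the only band next to a woman at 125 months is the third, and no competing table has a claim on her. The protocol does not say that table choice would be improvised; it gives the task to the pharmacist and the statistician together. The number of people who know the assignments is a separate feature of the plan, and a different top bound would not alter it. For the shared endpoints at 40 and 80 months, either table keeps the blocked 2:1 allocation.

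The Background wording is no reason to reopen eligibility. It is rationale, not a criterion, and counted in completed years it agrees with 10 years 11 months. The two places that set the limit say the same thing.

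**Conclusion.** The printed strata stop 11 months short of the eligibility limit, but this is a clerical slip that those running the randomisation would fill sensibly by using the third table. On that reading the 2:1 ratio, sample size, power and planned analyses are unchanged, and no bias arises. The only effect is a third band of 51 months instead of 40. A separate fourth table would cost about 0.01 SD at most in expected balance.

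The number of women affected cannot be known from the documents. The figures of 0.3 and 3.5 of 42 rest on assumed recruitment shapes, and the larger is nearer an upper figure. The conclusion does not depend on which shape is closer, because placing these women in the third table is harmless under both. It would change only if they were allocated outside every table, which the plan does not suggest. Restating the bounds would be editorial tidying, with no gain in the trial's inference.

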#### 3. Key Exclusion Criteria

- 1. Currently smoking more than 10 cigarettes/day by self report;
- 2. History of clinical CVD including myocardial infarction, angina, or congestive heart failure;
- 3. History of thromboembolic disease (deep vein thrombosis or pulmonary embolus);
- 4. History of untreated (no cholecystectomy) gallbladder disease as per self-report during PE;
- 5. History of triglyceridemia by subject report;
- 6. Undiagnosed vaginal bleeding as per self-report;
- 7. History of estrogen responsive cancers as per self-report;
- 8. Known hypercoagulable state (thrombophilias) as per self-report;
- 9. Severe lactose intolerance (sham depletion requires lactose/microcellulose administration; mild to moderate lactose intolerance is acceptable); [name] will make the final decision whether an individual's lactose intolerance is severe enough to require exclusion;
- 10. Use of estrogen- or progestin-containing medication or phytoestrogen containing supplements (e.g. soy concentrates or extracts) within 3 months of participation as per self-report; foods containing soy (e.g. tofu, soy milk) will be permissible; estrogen-based localized treatments such as creams and vaginal inserts will be permissible, so long as said treatments do not effect systemic estrogen levels (women using localized treatments must have estrogen levels similar to other women in the study of their age and menopause status). PI will have final decision about enrollment (see note 3 below);
- 11. Have a Mini Mental Status Score of  $\leq$  25;
- 12. Hamilton Depression Score > 14;
- 13. As per self-report, have taken a psychotropic medication within the previous month, with the exception of sleeping aids if the participant is willing to forgo use during study participation;
- 14. Have a metallic implant as per self-report;
- 15. Are claustrophobic as per self-report;
- 16. Are pregnant (pertains to peri-menopausal women only).

Note 1: In the case of participants with full or partial hysterectomy, timing of final menstrual period will be determined by [name] (the study PI) or one of the study MDs. In cases in which final menstrual period cannot be established, subjects will be excluded from the study.

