For the peri- and post-menopausal women participating in our previous tryptophan depletion/estrogen study (Amin et al., 2006b), mean baseline estradiol level was 31.72 pg/ml. With the 0.10 - 0.15 mg/d estradiol dose, mean estradiol levels were 96.33 pg/ml. Thus, our goal is to achieve a similar increase in estradiol in subjects participating in the present study. These doses are higher than the lowest available and may be higher than the lowest effective dose, which is the standard in clinical practice. However, in this experimental context, it is necessary to have a significant increase in plasma estradiol level in order to evaluate estrogen's effects. In addition, the standard dose in clinical practice is recommended for long-term ET. The proposed short-term ET regimen (chosen to more closely mimic the cyclic regimens currently recommended) is not likely to be associated with as significant risks as long-term ET. In our previous study, although women with greater time since LMP were found to have lower pre-treatment estradiol levels, the relationship between time since LMP and estradiol was less negative following ET, suggesting increased similarity among participants. Nevertheless, we will control for both age and plasma estradiol level when examining effects of time since LMP.

Following completion of approximately 6 weeks of ET or PT, the subjects will participate in the last two TRP depletion test sequences (one sham and one active depletion). Upon completion of the 4th test day (or use of estrogen for at least 2 weeks in those who drop out), all subjects will be debriefed regarding their active vs placebo patch status and subjects randomized to ET will take Prometrium (micronized progesterone USP encapsulated with peanut oil) 200 mg daily or medroxy progesterone 5 mg/d (for women with peanut allergies) for 12 days. Prometrium and medroxy progesterone are USFDA approved for antagonism of estrogen effects on the endometrium in women taking hormone treatment (HT). According to a review of studies of oral progesterone in menopausal women, use of progesterone,

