the progestational steroid produced by the human corpus luteum, minimizes side effects seen with synthetic progestins (McAuley et al., 1996). Long-term protection of the endometrium by Prometrium given as 200 mg/day for 12 days/month or medroxy progesterone given as 5 mg/d has been established (Gibbons and Thorneycroft, 1999). Oral micronized progesterone at a dose of 200 mg/ day is well-tolerated, with the only specific side effect being mild and transient drowsiness. Those women who would like to continue hormone therapy will be prescribed 3 additional months of estrogen (as well as an additional Prometrium treatment for women who have an intact uterus) and then referred to their gynecologist for continued treatment. The participant or her insurance company will be responsible for covering the cost of the additional treatment. Those women who wish to discontinue their HT will do so after cycling themselves with Prometrium or medroxy progesterone for 12 days. After the 12 days of Prometrium or medroxy progesterone with the Vivelle patch, women will discontinue both hormones.

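### The first 12-day progestogen course carries no intact-uterus condition, so an ET woman without a uterus takes a drug with no stated benefit to her and stays on the patch to accompany it

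*Combined protocol and SAP*

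**What the plan says.** The rule is in the combined protocol and SAP, under Randomization to Estrogen Treatment (ET) or Placebo Treatment (PT). Once the fourth test day is done, "subjects randomized to ET will take Prometrium (micronized progesterone USP encapsulated with peanut oil) 200 mg daily" for 12 days, with medroxyprogesterone 5 mg/day for those with a peanut allergy. The trigger also covers "use of estrogen for at least 2 weeks in those who drop out". Peanut allergy is the only branch.

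The reason given is endometrial: "Prometrium and medroxy progesterone are USFDA approved for antagonism of estrogen effects on the endometrium". The same subsection then refers to long-term endometrial protection and gives no other purpose.

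On stopping, it says: "Those women who wish to discontinue their HT will do so after cycling themselves with Prometrium or medroxy progesterone for 12 days". The patch stays on meanwhile: "After the 12 days of Prometrium or medroxy progesterone with the Vivelle patch, women will discontinue both hormones".

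Women who prefer to continue receive three more months of estrogen, "as well as an additional Prometrium treatment for women who have an intact uterus". That is the only place where uterine status decides who gets progestogen.

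Women with a hysterectomy are not barred. Note 1 under Key Exclusion Criteria begins "In the case of participants with full or partial hysterectomy, timing of final menstrual period will be determined by" the PI or a study MD, and excludes them only if that date cannot be established.

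**The concern.** The plan gives a drug by treatment arm when its stated reason applies only to women who have an endometrium. The authors recognised this for the additional course, so the missing condition on the first course looks like an oversight. No reason for the difference is given.

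What is at stake is avoidable exposure of participants. Section 1 (Risks) of the Risk/Benefit Assessment lists breast tenderness, bloating, fluid retention and depression for both progestogens. Depression is relevant because the inclusion criteria admit women whose major depression resolved more than three years ago. The same section says the added stroke and clot risk exists from the start of estrogen use. For a woman who has no uterus and wants to stop, the patch is continued through a course that has no stated purpose for her.

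**Working it through.** There is no planned figure to reproduce. The check compares the provisions and counts days.

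**Provisions side by side**

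| Provision | Who it covers | Uterus condition |
|---|---|---|
| First progestogen course | All ET completers, and ET dropouts with at least 2 weeks of estrogen | None |
| Additional course | ET women who continue hormones | Intact uterus |
| Eligibility, Note 1 | Full or partial hysterectomy | Excluded only if the final period cannot be dated |

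An ET woman without a uterus can therefore be enrolled, and the first-course rule applies to her as written.

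**Progestogen per woman**
- Prometrium: 12 × 200 mg = 2,400 mg.
- Medroxyprogesterone: 12 × 5 mg = 60 mg.

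**Patch days for a completer who wants to stop**
- Stated patch duration (Method for Assigning Subjects to Groups, and the Randomization subsection): 8 × 7 = 56 days.
- Test Days 3 and 4 (Study Procedures, Detailed Description): one week apart after about 6 weeks, so Test Day 4 falls near day 42 + 7 = 49.
- End of the 12 days: 49 + 12 = day 61.
- Within the 8 weeks: 56 − 49 = 7 days. Beyond: 61 − 56 = 5 days.
- Estradiol beyond the 8 weeks: 5 × 0.10 = 0.5 mg, or 5 × 0.15 = 0.75 mg. The Randomization subsection gives 0.10 mg/day where it assigns treatment. The assignment section gives a range up to 0.15.

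The split depends on timing, because the 6 weeks are approximate. Days beyond the regimen = max(0, T + 12 − 56), where T is the day of Test Day 4. This gives 0 at T = 44, 5 at T = 49 and 12 at T = 56.

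**Patch days for a dropout**

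At the minimum of 2 weeks, 14 + 12 = 26 days of estrogen. That is inside 56 days, but all 12 added days come after she has left the study.

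**How many women**

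The documents give no hysterectomy share. As an assumption only, take a share p of the 28 ET women (Objectives, Specific Aim 2). The expected number is 28p and the chance of at least one is 1 − (1 − p)^28.

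| Assumed p | Expected women | Chance of at least one |
|---|---|---|
| 2% | 0.56 | 0.432 |
| 10% | 2.8 | 0.948 |
| 20% | 5.6 | 0.998 |

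These counts take in full and partial hysterectomy alike and do not separate women who want to stop from those who continue.

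**Effect on outcomes**

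The course starts after Test Day 4 or after dropout, so no study measurement follows it.

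**The case against.** The strongest objection concerns the estrogen. A reader might infer that all 12 patch days are surplus to the plan. The documents do not support that: the patch is prescribed for 8 weeks, and for a completer about 7 of the 12 days fall inside that period. This stands, and the excess over the stated regimen is about 5 days. It also means that telling women to stop at Test Day 4 would contradict the stated duration unless that wording changes too.

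Second, a partial hysterectomy may leave tissue, so one cannot infer that progestogen is pointless for every woman covered by Note 1. This also stands. The point is firmest for full hysterectomy, and partial cases need a physician's judgement.

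Third, clinical oversight makes mechanical application less likely. A study physician already reviews each hysterectomy history to date the final period. Early Withdrawal of Subjects provides a talk with the PI about staying on estrogen, and all subjects are debriefed at this stage. This has some force, but none of these steps mentions uterine status or waives the course. Where the authors wanted a branch, they wrote one.

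Fourth, the harm is small. For micronized progesterone the plan cites "the only specific side effect being mild and transient drowsiness", and the long-term risks it describes concern use over about five years. The regimen is short with or without these days. This stands and limits the weight of the point. The consent pages are not in the copy reviewed, so what women are told about the course cannot be checked.

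**Conclusion.** The point holds as a matter of participant safety and is a cheap improvement. As written, an ET woman without a uterus takes 12 days of progestogen with no stated benefit. If she wants to stop, she also stays on the patch for 12 days after her last study measurement. For a completer about 5 of those days run past the stated 8 weeks (about 0.5 to 0.75 mg estradiol, assuming Test Day 4 near day 49). For a dropout all 12 follow withdrawal.

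The number of such women is unknown, and the counts above rest entirely on assumed shares. Harm per woman is likely small. A reader might also infer some bias in the trial's comparisons. There is none from this source, because no outcome is measured after the course begins.

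**What to change.** 1. In the Randomization subsection, limit the first progestogen course to ET subjects *who have an intact uterus*, the condition already used for the additional course. State that the study MD decides for women with a partial hysterectomy, from the gynecologic history taken at intake.
2. In the text on stopping, add that women without a uterus who do not wish to continue hormones stop the patch after Test Day 4, or at withdrawal, and in any case by the end of the 8 weeks, without progestogen.
3. In Method for Assigning Subjects to Groups and in the Randomization subsection, word the patch duration as *up to 8 weeks*, so that it agrees with step 2.

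The cost is minor wording edits. No visit, test or participant is added, and the analysis does not change.
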